7.2.4 Time to Last Treatment Failure

TLTF will be summarized using the Kaplan-Meier method. Percentiles of survival curve (25%, median and 75%) with their 2-sided 95% CIs will be estimated. Yearly rates with their 2-sided 95% CI will also be provided. Censor rule is the same as that described in Section 7.2.1.

7.2.5 Baseline Characteristics

Baseline characteristics will be summarized descriptively. Similarly, patient's characteristics at the start of lorlatinib treatment will be summarized descriptively.

The third-line or later regimen data will be listed if the lorlatinib treatment is the second-line therapy. Similarly, the second-line regimen data will be listed if the lorlatinib treatment is the third-line or later therapy.

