8.2. Secondary objectives

The secondary objectives are as follows:

- To describe treatments received including alectinib as a first-line treatment prior to lorlatinib
- To describe treatment pattern after lorlatinib as a second/later-line treatment

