9.3. Variables

9.3.1. Patient characteristics at baseline

All included cases will be treated with lorlatinib (exposure). Variables for patient characteristics, treatment and outcomes are presented in [Table 1](#)

Variables planned at the baseline will be collected at the time of obtaining the informed consent as much as possible.

Table 1 Key variables of interest and data collection timepoints.

Role	Variable	Timepoint			
		Baseline	Initiation of lorlatinib	Subsequent follow-up visits	End of observation period
Patient characteristics	
 • Age • Sex • Weight • Height • Smoking status (Current smoker, Former smoker, Never smoker) • Brinkman index • ECOG PS (Grades 0 to 5)^a • Date of initial NSCLC diagnosis • Date of advanced NSCLC (TNM stage IIIb-IV) diagnosis • NSCLC histopathological subtype • Clinical NSCLC staging (based on Tumor, Node and Metastasis, TNM)^b • Presence and location of metastasis (including central nervous system, CNS) at initial diagnosis and lorlatinib initiation • Complications/medical history (related to history of treatment for ALK+ NSCLC) • Date of ALK testing • Method of ALK testing • Alectinib initiation date • Alectinib discontinuation date • Presence and location of metastasis (including central nervous system, CNS) during Alectinib treatment • Presence of treatment for some metastasis (including 	X	X	(X) ^c	

PFIZER CONFIDENTIAL

Role	Variable	Timepoint			
		Baseline	Initiation of lorlatinib	Subsequent follow-up visits	End of observation period
	CNS) during Alectinib treatment, and type of treatment(i.e. Radiation Therapy)				
	
 • Reason for alectinib discontinuation • second-line treatment start/end date and drug name, reason for the discontinuation, if lorlatinib is 3rd line treatment 			X	
Treatment	
 • Line for lorlatinib • Lorlatinib initiation date • Dose of lorlatinib • Lorlatinib discontinuation date • Reason for lorlatinib discontinuation • Third-line or later treatment start and end dates, if lorlatinib is second or later line treatment. • Reason for Third-line or later discontinuation, if lorlatinib is second or later line treatment. 		X	X	X ^d

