9.3.3. Objective Response

Definitions of objective response are defined in [Section 9.1.3](#). The following data will be collected: tumor response, and date of tumor response assessment.

Best objective response will be assessed based on reported overall responses at different evaluation time points from each initiation of treatment therapy until discontinuation.

9.3.4. 3rd-line/later line regimen after lorlatinib or pretreatment regimen before lorlatinib treatment

The following 3rd/later-line regimen data will be collected, if lorlatinib treatment is the second line setting: medication, initial date of administration, and reason for discontinuation.

The following second-line regimen data will be collected, if lorlatinib treatment is 3rd/later-line setting: medication, initial date of administration, and reason for discontinuation.

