2.2 STUDY OBJECTIVES

The primary objective is to describe the demographic characteristics of patients with *ALK*⁺ NSCLC patients treated with lorlatinib as the second-line or later therapy after failure of alectinib as the first-line therapy in a real-world clinical setting, clinical usage and observed effectiveness of lorlatinib.

The secondary objectives are as follows:

- To describe treatments received including alectinib as the first-line therapy prior to lorlatinib
- To describe treatment pattern after lorlatinib as the second-line or later therapy

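### The SAP lists regimens after lorlatinib only when lorlatinib was second line, although the secondary objective covers second- and later-line lorlatinib

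*SAP*

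**What the plan says.** The objective has the same scope in both documents. Protocol 8.2 has "To describe treatment pattern after lorlatinib as a second/later-line treatment" and SAP 2.2 has "To describe treatment pattern after lorlatinib as the second-line or later therapy". Neither limits it to second-line lorlatinib.

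SAP 7.2.5 sets two listing conditions. For treatment after lorlatinib: "The third-line or later regimen data will be listed if the lorlatinib treatment is the second-line therapy". For the other patients: "the second-line regimen data will be listed if the lorlatinib treatment is the third-line or later therapy".

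Protocol 9.3.4 divides collection in the same way. Regimens at third line or later are recorded "if lorlatinib treatment is the second line setting: medication, initial date of administration, and reason for discontinuation". For the rest, "The following second-line regimen data will be collected, if lorlatinib treatment is 3rd/later-line setting".

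Table 1 in protocol 9.3.1, titled "Key variables of interest and data collection timepoints", is wider in one respect. It asks for start and end dates and discontinuation reasons of third-line or later treatment when lorlatinib was second line or later. It has no drug name in those items. The only drug name it requests, apart from lorlatinib and alectinib themselves, is in "second-line treatment start/end date and drug name, reason for the discontinuation, if lorlatinib is 3rd line treatment". Its outcome row on treatment after lorlatinib mentions second-line lorlatinib only.

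SAP 7.2.1 plans time to treatment failure (TTF) of subsequent other treatment separately for each lorlatinib line, with chemotherapy and other TKIs as examples. SAP 7.2.6 summarises discontinuation reasons.

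**The concern.** Which drug comes next is the core of a treatment pattern. The objective asks for that pattern after lorlatinib at second or later line, but the listing that would show it is conditioned on second-line lorlatinib. For a patient who had lorlatinib at third line or later, the corresponding listing gives a regimen received before lorlatinib, which serves the other secondary objective.

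If the plan is followed literally, the report can say how long treatment lasted after third- or later-line lorlatinib and why it stopped, but has no planned output saying what it was. A TTF for an unspecified mix of later treatments is hard to interpret. The pattern by drug would be described for one of the two line groups that the objective covers. The study is purely descriptive and its rationale is the lack of real-world information on treatment sequences that include lorlatinib, so this is a gap in what it sets out to deliver.

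**Working it through.** No stated figure is in dispute, so the check compares the objective, the collection rules and the planned outputs for treatment given **after** lorlatinib.

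| Place | Lorlatinib second line | Lorlatinib third line or later |
|---|---|---|
| Objective (protocol 8.2, SAP 2.2) | covered | covered |
| Protocol 9.3.4, medication | specified | not specified (second-line regimen only) |
| Table 1, dates and discontinuation reason | specified | specified |
| Table 1, drug name | not specified | not specified |
| Table 1, outcome row for TTF of later treatment | specified | not specified |
| SAP 7.2.1, TTF of subsequent treatment | planned | planned |
| SAP 7.2.6, discontinuation reasons | planned | planned |
| SAP 7.2.5, regimen listing | planned | not planned (second-line regimen only) |

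The right-hand column gives dates, durations and reasons but no drug. The left-hand column gets the drug from protocol 9.3.4 and SAP 7.2.5, the two places where the condition is narrower than the objective.

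The change history in SAP section 1 shows that version 2 clarified that TTF of subsequent treatment is summarised by each lorlatinib line. The wider scope was therefore made explicit for durations, while the listing condition in 7.2.5 still names second-line lorlatinib alone.

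A related gap precedes lorlatinib. If lorlatinib was fourth line or later, only the second-line regimen is specified and listed, so the drugs in the lines between it and lorlatinib are not. The number of such patients is not given and may be zero.

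**Size.** Inputs are from protocol 9.5 and SAP 2.1.1: about 50 patients in total, about 30 with second-line lorlatinib.

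- Third line or later: 50 − 30 = 20 patients; 20/50 = 40%.
- Only those treated again after lorlatinib have a regimen to list. The documents give no rate r, so the number affected is 20 × r: 0 patients at r = 0 and 20 at r = 1, that is 0 to 40% of the cohort.
- The counts are flexible. Assuming 35 second-line patients of 50, the upper limit is 50 − 35 = 15 (30%). Assuming 25, it is 50 − 25 = 25 (50%).

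**The case against.** The strongest reply is that the text does not exclude anything. SAP 7.2.5 says when later regimens will be listed; it does not say that no others will be. Protocol 9.7.1 promises a description of treatment patterns for all lorlatinib patients, and SAP 7.1 summarises any categorical variable. This is a fair reading of intent, but no section actually plans an output by drug after third- or later-line lorlatinib.

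Second, the data may well exist. Table 1 covers only key variables, and it omits the drug name even after second-line lorlatinib, where protocol 9.3.4 does collect it, so its silence proves little. TTF of subsequent treatment by lorlatinib line, combined TTF (SAP 5.1.2) and time to last treatment failure (SAP 5.1.4) all need later treatments recorded in every patient. The CRF was not available. This stands: the finding concerns what the documents specify and does not show that the drug names are missing. If they are in the database, only the listing condition needs to change.

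Third, the effect is small and the timing late. It touches drug identity in a listing for part of a descriptive secondary objective, no estimate changes, and the number affected could be zero. Data collection was due to end on 31 Oct 2021 and protocol amendments need ethics approval (protocol 10.4), so rewriting collection rules may be moot. This limits the remedy, but it does not remove the mismatch between objective and listing.

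**Conclusion.** The concern holds. The planned regimen listing is narrower than the secondary objective, and neither document specifies collecting the drug given after third- or later-line lorlatinib. At the planned counts, up to about 20 of 50 patients (40%) would have post-lorlatinib regimens left unlisted; the range is 0 to 20, because no rate of further treatment is given. With assumed second-line counts of 35 or 25, the top of the range is 15 or 25. The conclusion assumes that the SAP is followed as written and makes no claim about the CRF. Durations, dates, discontinuation reasons and the primary endpoint, including lorlatinib TTF, are unaffected. The change should be made because it is cheap and closes a gap against a stated objective; the main results do not depend on it.

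**What to change.** Replace the two conditional sentences in SAP 7.2.5 with one: *All regimens before and after lorlatinib will be listed for every patient, by line of lorlatinib.* This also covers the lines between second line and a fourth- or later-line start of lorlatinib.

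If the database is still open, align protocol 9.3.4 and Table 1 so that medication, start and end dates and discontinuation reason are specified for each regimen whatever the lorlatinib line, and remove the second-line restriction from the Table 1 outcome row on treatment after lorlatinib. The cost is one drug-name field per regimen, the abstraction to fill it, and a protocol amendment.

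The lock was planned for 30 Nov 2021 and SAP version 3 is dated 12 May 2022. If lock took place as planned, first check whether the drug names are in the database. If they are, the only cost is the changed condition and a slightly longer listing. If they are not, list what was collected and state in the report that the pattern by drug after lorlatinib is described for second-line lorlatinib only. Neither route after lock requires going back to the charts.

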7.2.6 Reason for Discontinuation

Reason for discontinuation will be summarized.
